5.3 EXCLUSION CRITERIA

Participants who meet any of the following criteria, at baseline, are excluded from the study:

- As determined by the Site Investigator, any significant uncontrolled, active or chronic disease process such as but not limited to diabetes, hypertension, and other diseases involving the cardiovascular, pulmonary, gastrointestinal, genitourinary, musculoskeletal, and central nervous systems
- Confirmed \geq Grade 2 hypophosphatemia
- Presence of serious psychiatric symptoms (e.g., active hallucinations)
- Visibly distraught at the time of consent (e.g., suicidal, homicidal, exhibiting violent behavior)
- Intoxicated or under the influence of alcohol or other drugs at the time of consent
- Acute or chronic hepatitis B infection (i.e. if hepatitis B surface antigen positive)
- Hep B seronegative and refuses vaccination.
- Renal dysfunction (Creatinine Clearance < 75 ml/min);
(Use Cockroft-Gault equation:

$$\text{Male} \quad \frac{(140-\text{age}) * \text{Weight(Kg)}}{\text{Serum Creatinine (mg per dl)} * 72} = \text{ml/min}$$

$$\text{Female} \quad \frac{(140-\text{age}) * \text{Weight(Kg)}}{\text{Serum Creatinine (mg per dl)} * 72} = \text{ml/min} * 0.85$$

Serum Creatinine conversion Factors

$$\text{Creatinine (mg/dl)} = \text{Creatinine (\mu mol)} / 88.4$$

$$\text{Creatinine (mg/dl)} = \text{Creatinine (mmol)} / 88.4 * 1000$$

- Urine dipstick for protein and glucose, excluding 1+ or greater
- Any history of bone fractures not explained by trauma
- Any Grade ≥ 2 toxicity on screening tests and assessments
- Concurrent participation in an HIV vaccine study or other investigational drug study
- Known allergy/sensitivity to the study drug or its components
- Use of disallowed medications (see section 6.5)

Note: Otherwise eligible participants with an exclusionary test result may be re- tested during the screening process. If a participant is re-tested and a non- exclusionary result is documented within 40 days of providing informed consent for screening, the participant may be enrolled.

5.4 STRATEGIES FOR RECRUITMENT

Adolescents will be recruited through community outreach, by targeting schools, youth groups, sport clubs, taxi ranks, and other points of convergence in the community. In addition, local HCT centres and primary health care clinics will be targeted. Well-established relationships with community stakeholders exist at both proposed study locations and these will be capitalised on.

DTHF's adolescent CAB has also assisted researchers in developing strategies to enhance adolescent participation in studies. The Future Fighters have assisted with the development of many stakeholder engagement initiatives, aimed at strengthening recruitment and retention mechanisms, including drama, poetry, rap, song, and dance performances in their local settings. Media is also widely incorporated into their recruitment strategies, including MXIT, Facebook and other social networks.

5.5 STRATEGIES FOR RETENTION

Given the study sites' previous experience with the South African Studies on HIV in Adolescents (SASHA) Project, funded by the EDCTP, the study staff have an in-depth understanding of youth friendly health services, age-appropriate counseling techniques, and adolescent-specific recruitment and retention strategies. Attempts will also be made to engage adolescent participants in a number of activities, including pairing participants with one another to offer support and encouragement to complete the study, where adolescents are willing to do so.

Other mechanisms that will be used during the study, to ensure maximum retention, such as:

- Collection of detailed locator information at the study screening visits, and active review and updating of this information at each subsequent visit
- Use of visit reminder strategies (these have been tried and tested by this adolescent community and are acceptable)

- Follow-up on missed visits
- Mobilization of trained outreach workers to assist with follow up
- Regular communication with the study community at large to increase awareness of HIV and explain the purpose of HIV prevention research in adolescent populations and the importance of completing research study visits

5.6 CO-ENROLLMENT GUIDELINES

Co-enrollment in other research studies, which do not involve investigational agents or active study products or medical devices, is permitted.

6 STUDY PRODUCT

6.1 REGIMEN

The regimen for enrolled study participants who choose to receive the study product during the 12 months of follow up is a FTC/TDF (Truvada®) tablet taken orally, once daily. For any missed doses, participants will be instructed to take the next scheduled dose.

6.2 FTC/TDF FORMULATION

FTC/TDF or Truvada® is a 200mg/300mg fixed dose combination tablet containing emtricitabine (FTC) and tenofovir disoproxil fumarate (TDF). FTC is a synthetic nucleoside analogue of cytidine. (See Section 2.4: Study Products). One FTC/TDF tablet contains 200 mg FTC plus 300 mg of TDF. FTC/TDF should be stored at 25°C. Excursions are permitted between 15°C and 30°C.

6.3 STUDY PRODUCT SUPPLY AND ACCOUNTABILITY

FTC/TDF tablets will be supplied by Gilead Sciences (Foster City, CA, USA). FTC/TDF tablets (30 tablets per bottle) are packaged in bottles with a child-resistant screw cap. In addition to the tablets, each bottle contains a silica gel desiccant to protect the product from humidity and polyester packing material that cushions it during handling and shipping. Gilead will prepare bottles of study agent that are each labeled with the active agents and the expiry date.

6.3.1 Pharmacy Facilities and Drug Dispensing

A pharmacist will be responsible for dispensing the drug to each study participant. Only participants with negative HIV test results, will be dispensed the study drug. At enrollment, participants who take study medication will receive a prescription that will include the participant ID. Detailed instructions for receipt, handling, storage, dispensing, accountability, retrieval of unused study products from participants will be provided in site-specific SOPs and South Africa's Good Pharmacy Practice Guidelines.

6.3.2 Retrieval of Unused Study Drug

The study pharmacist will document all product returns and store any unused study product

in a designated area of the pharmacy. At the end of the study, any unused product will be destroyed, per GCP guidelines and instructions received by Gilead Sciences.

6.4 STUDY PRODUCT ADHERENCE ASSESSMENT

Adherence to study product will be measured by the use of self-report, pill counts, and proportion of participants on FTC/TDF who have detectable drug levels.

Comprehensive and age-appropriate study product adherence counseling will be provided to all study participants who receive study product, at every visit (until week 48,) to help ensure high rates of study product use. Counseling will address such topics as personal barriers and facilitators to using PrEP, remembering to use the study product daily, reminders to contact study staff with questions about study product use, and not to distribute or share their study products to other people. The current client centered counseling methodology applied by both sites for the FACTS 001 study (both sites are involved in this adult microbicide study) is being adapted for adolescent appropriateness and will be applied in this study. This will also be adapted to include or not include (depending on participant choice) the incorporation of drug level data back to the participant. It is envisaged that the adaptation will include modifications around daily use vs BAT24 (regimen in FACTS001), Oral PrEP vs topical and a youth centered approach vs an adult approach. It will have all the elements of being client centered, with emphasis on finding barriers and facilitators of adherence in a non-judgemental approach.

For the participants who select biofeedback during counseling, results from blood plasma or dried blood spots, which indicate their drug levels, will be fed back to participants at scheduled follow up visits. Participants may choose differently at each feedback session. In cases where drug levels indicate overuse study staff will be informed to intervene.

6.5 CONCOMITANT MEDICATIONS AND PROCEDURES

With the exception of medications listed as prohibited (see below, this section), enrolled study participants may use concomitant medications during study participation. All concomitant medications, including prescribed and over-the-counter Preparations, vitamins and nutritional supplements, recreational drugs, and herbal Preparations reported within the 70 days prior to study enrollment and throughout the course of the study will be recorded on the Case Report

Forms (CRF) designated for that purpose. Medications used for the treatment of AEs that occur during study participation also will be recorded on applicable study case report forms.

Should participants report use of any of the following medications, they will be required to discontinue use of study drug: interleukin therapy, medications with significant nephrotoxic potential (including but not limited to amphotericin B, aminoglycosides, cidofovir, foscarnet and systemic chemotherapy), and medications that may inhibit or compete for elimination via active renal tubular secretion (including but not limited to probenecid). In addition, if a participant requests post-exposure prophylaxis (PEP) for HIV exposure, they will be referred to a health care provider for evaluation. If a participant starts ARV therapy for PEP, they should hold study medications until completion of the course of PEP.

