Design	
The study is designed as an open-label, single arm cohort study, to evaluate the Acceptability, safety and Use of daily oral PrEP (FTC/TDF) in 150 adolescents (approximately 75 participants at each site), ages 15-19 years, their adherence to study product, and any changes in their sexual and health behaviors over a 12-month (52 week) period. All participants will complete an initial (12 week) 3- month period, during which they will receive PrEP as part of a combination prevention package. At all subsequent visits, participants will be offered the opportunity to hear real-time feedback of drug level data as part of their adherence counseling or they may choose to have adherence counseling without the feedback of drug level data. The decision about feedback as well as self reported adherence will be captured via interviewer administered questionnaires at each follow up visit. At the first 3 month (week 12) visit and 3 monthly (weeks 24, 36, 48) intervals thereafter participants will be offered the following options: full package + PrEP, stop PrEP and continue with rest of package or alternatively re-start PrEP if previously stopped. This will occur during protocol-specified study visits.
 
Participants will be followed regardless of PrEP usage for a total of 12 months (52 weeks). PrEP may be stopped at any other clinic visit but recommencement can only occur at a scheduled visit when all medical criteria are met including a negative HIV test. Adherence counselling will be offered at every visit with options to have drug level feedback or not as part of this counselling.

Study site	The study will be conducted at The Desmond Tutu HIV Foundation research site in Masiphumelele, Cape Town and the Perinatal HIV Research Unit (PHRU) site in Soweto, near Johannesburg.
Study drugs	FTC/TDF or Truvada® is a 200mg/300mg fixed dose combination tablet containing emtricitabine (FTC) and tenofovir disoproxil fumarate (TDF).
Study population	Healthy, HIV-uninfected adolescents, 15 and 19 years of age
Number of participants	150 enrolled participants (approximately 75 participants at each site)

Treatment Regimen	Participants will be provided with a supply of FTC/TDF tablets, taken orally, once daily for first 3 months. Thereafter, these tablets will only be supplied to those who indicate willingness to take PrEP and who do not have a clinical contraindication to do so.

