for continuing or stopping PrEP. A short acceptability questionnaire will also be administered. This opportunity to “opt out” or “opt back in” will occur at 3 monthly visits until Week 36. Followup will continue until week 48. Those who opt out at a 3 monthly visit will be asked whether they wish to restart at the next 3 monthly visit. Participants will also be advised that they may “opt out” of PrEP in their prevention package at any scheduled visit or at any time in consultation with clinic staff. They will be expected to return all study product and will not be issued TDF/FTC. They may “opt back in” on a subsequent study visit if all eligibility criteria are met and after a negative HIV test is obtained. At each study follow up visit, participants will be asked to grade their adherence on a visual scale, they will also be asked whether they wish to receive drug levels and their response and reasons for this will be captured. They will then receive motivational adherence counseling with or without drug levels depending on their choice at the time. Monthly scheduled visits will occur until month 3, thereafter scheduled visits will be 3 monthly.

Whilst every effort will be made to encourage adherence to PrEP in the first 3 months, poor adherence during those months will NOT preclude participation after 3 months. Every effort will be made to ascertain level of use and reasons for less than optimal use.

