- Study drug supplies and instructions/counseling (for participants who choose to receive study product)
 - At all visits where study product is administered week 12, 24, 36
- Reimbursement
 - At all visits
- Schedule next visit
 - At all scheduled visits, except Final Study Visit
- Clinical Procedures
 - Contraceptive counselling and provision as appropriate
 - At all visits
 - Physical exam
 - At week 48
 - As clinically indicated
 - Update medical and menstrual history and/or current medications if applicable

- At all visits
- Record/update adverse events (AEs) applicable
 - At all visits
- Laboratory Procedures
 - HIV rapid testing
 - At all visits
 - As clinically indicated at unscheduled visits (reported exposures)
 - STI testing
 - Herpes (HSV-2),
 - Chlamydia, and Gonorrhea testing (0, 12, and 48 weeks)
 - Urine dip stick testing
 - Every 12, 24, 36, 48 weeks
 - Aspartate aminotransferase/alanine aminotransferase (AST/ALT) testing
 - Every 12, 24, 36, 48 weeks
 - Serum chemistries, including creatinine, glucose, electrolytes, and lipase
 - Every 12, 24, 36, 48 weeks
 - Full Blood Count testing
 - Every 12, 24, 36, 48 weeks
 - Urine pregnancy testing (for females)
 - At all visits
 - Contraceptive counseling
 - At all visits
 - Measurement of study drug levels by Plasma/DBS
 - At 12, 24, 36, 48 weeks.

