7.5 INTERIM VISITS

Participants may make interim contacts and unscheduled visits at their request, or as deemed necessary by the Site Investigator or designee, at any time during the study. All interim contacts and unscheduled visits will be documented in the participant's study file. When an interim contact or unscheduled visit occurs in response to AEs, a study clinician will clinically assess the reported

event and provide, or refer the participant for, appropriate medical care. Study participants will be instructed to contact their study clinic in the event of any AE. Participants will also be instructed to seek immediate emergency care (even from other providers) if they consider they require it. The AE will be reported on the appropriate CRF.

Some examples of reasons for an interim visit are:

- To report an AE;
- To get more condoms or study product;
- To address any contraceptive needs;
- To ask questions of study staff;
- To discuss problems with study adherence;
- To perform an interim examination (e.g., follow-up on an AE or participant request); and
- To provide lab results not available at the last follow-up visit.

If a participant is contacted when s/he missed a visit, staff will try to obtain her reasons for missing a visit. This information may be used to try to improve overall retention in the study.

7.6 FINAL STUDY VISIT (WEEK 52) OR TERMINATION VISIT (AND AT THE TIME OF ANY PERMANENT STUDY PRODUCT TERMINATION OR STUDY PRODUCT DISCONTINUATION)

Participants who reach week 52 will follow procedures included in the table of study procedures on page 72. This includes provision of any outstanding test results and final interviews. In addition a DBS/ plasma will be performed for drug levels at the final study visit.

Participants who have chosen to discontinue the product prior to the routine protocol-required withdrawal at Week 52 should continue routine follow-up visits. All protocol-required interviews and procedures, besides study product administration and drug levels, should be continued until Final Study Visit.

If a participant discontinues study product following instruction from the Investigator or wishes to withdraw permanently from the study, visit procedures as per week 48 will be conducted. The participant will then return for a final study visit (week 52) if possible.

The following procedures will be completed the final visit (wk 52 the final visit):

- Administrative/Behavioural Procedures
 - Locator information (update)

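### Section 6.5 ends the product hold for PEP at completion of the PEP course, with no HIV test, visit or tablet return named, whereas the Protocol Summary allows recommencement only at a scheduled visit with a negative HIV test

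*Protocol*

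**What the plan says.** Section 6.5 sends a participant who asks for PEP to a health care provider and then gives the product rule for those who begin antiretrovirals as PEP: "they should hold study medications until completion of the course of PEP". That is the whole rule.

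The Protocol Summary (Design) allows PrEP to be stopped at any other clinic visit but adds that "recommencement can only occur at a scheduled visit when all medical criteria are met including a negative HIV test".

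Section 4.1, on participants who opt out, has them hand back all product. They may opt back in "on a subsequent study visit if all eligibility criteria are met and after a negative HIV test is obtained". Section 4.3 similarly makes continuing or restarting at the three-monthly visits depend on a negative test.

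Section 6.3.1 governs supply: "Only participants with negative HIV test results, will be dispensed the study drug".

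Section 7.10 sets procedures for participants who hold or discontinue product. Its subsections cover HIV infection, pregnancy, hepatitis B and the participant's own choice. PEP is not among them.

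**The concern.** Someone who starts PEP has just reported a possible HIV exposure. PEP is also a stated part of the prevention package, so the plan foresees this event. A site working from 6.5 could treat the end of the course as the end of the hold. A site working from the Summary would wait for the next scheduled visit and a negative test. The same participant would be managed in two ways, and under the first a recently exposed participant could take product again before anyone has confirmed that she or he is uninfected.

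**Working it through.** The plan gives no figure on this point, so there is none to reproduce. The check compares the texts and then does simple arithmetic on the visit schedule.

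**Does another passage supply the missing condition?**

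- *Dispensing (6.3.1).* The negative-test rule applies when product is handed out. In the optional-use period product is supplied at weeks 12, 24 and 36 (7.4), so a participant on hold may have most of a 12-week supply at home. Section 4.1 asks for tablets back on opt-out; 6.5 does not ask for them on a PEP hold.
- *Testing at unscheduled visits (7.4).* HIV testing for reported exposures is allowed as clinically indicated. It is not tied to the end of PEP or to resumption.
- *HIV testing at every visit (7.8).* This helps only if there is a visit between the end of PEP and resumption, and 6.5 names none.
- *PSRT (9.1 and 10.5).* Section 9.1 puts any discontinuation and potential resumption under PSRT consultation, and 10.5 has the PSRT decide where resumption awaits its advice. Neither names an HIV test, and 6.5 does not refer to the PSRT.

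None of these requires a negative result before a participant resumes from tablets in hand.

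**How long could product be taken before the next scheduled test?**

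Inputs: visits after week 12 are 12 weeks apart, with a window of 7 days either side (7.4). The documents do not give the length of a PEP course, *d*, so 14, 28 and 42 days are assumed as a range.

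- Target interval: 12 × 7 = 84 days.
- Longest interval with windows: 84 + 7 + 7 = 98 days.
- If PEP starts just after a visit, the time from the end of the hold to the next scheduled test is 84 − *d*, or at most 98 − *d*.

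| Assumed *d* (days) | 84 − *d* | 98 − *d* |
|---|---|---|
| 14 | 70 | 84 |
| 28 | 56 | 70 |
| 42 | 42 | 56 |

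Tablets could last that long. If 84 are supplied for the interval (an assumption, as the number dispensed is not stated) and the hold starts at once, about 84 remain when it ends. The largest number needed in the table is 84.

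Under the Summary rule the corresponding time is 0 days, because restart itself needs a scheduled visit and a negative test.

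In the first 12 weeks visits are 28 days apart, so a 28-day course ends at about the next visit (28 − 28 = 0) and a 14-day course leaves 28 − 14 = 14 days, before windows.

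**The case against.** The strongest reply is that nothing here conflicts. Section 6.5 can be read as setting only how long the hold lasts, with the Summary's conditions applying on top. Alternatively, the Summary sentence sits in an account of elective stopping and restarting, and medical holds follow other rules. Several holds in 9.1 end on laboratory results or PSRT approval without waiting for a scheduled visit. On that view 6.5 is merely silent.

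Much of this stands. Sections 4.1 and 4.3 concern elective opting out and back in, so the direct conflict is with the Summary alone. But neither reading removes the need for a change. If the Summary governs every recommencement, 6.5 is incomplete and differs from it on timing and conditions. If it does not, no passage requires a negative test before resumption from tablets in hand after PEP.

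The safeguards also deserve credit. A PEP request is a reported exposure, and PSRT consultation is worded broadly. PEP referral follows national policies (13.3), which are not before us. Most of the follow-up HIV algorithm (16.7) did not survive text extraction, so it could not be checked.

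Three stronger inferences are tempting but not supported:

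- *That interim visits open a second route to untested product.* Section 7.5 lists "To get more condoms or study product" among examples of reasons to attend. It is not a dispensing rule, and 6.3.1 requires a negative result for any dispensing.
- *That the background shows resistance arising in this situation.* The resistance cases on active drug in 2.6.7 were infections already present at enrolment. For iPrEx, the same section reports no resistance among those infected during the study.
- *That endpoints shift.* The Use analysis (10.6 and SAP) counts any self-reported use in an interval, regardless of adherence. A hold and restart within one interval would usually leave that unchanged. Any effect on total time on PrEP cannot be quantified from the documents.

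**Conclusion.** The point holds as a gap between 6.5 and the Summary. Section 6.5 does not instruct sites to restart product untested. It leaves that possible, because it states one condition for ending the hold and nothing else reaches tablets already in hand.

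The interval of 42 to 70 days (56 to 84 with the windows) is a worst case. It assumes PEP begun just after a visit from week 12 on, a course of 14 to 42 days, tablets kept at home, no test prompted by the exposure and no PSRT intervention. The long gap between scheduled tests applies to every PrEP user and is not created by 6.5. What is particular to PEP users is the recent exposure. Their number is unknown, and no sample size, precision or analysis figure changes. The case for acting is participant safety and consistent conduct between sites.

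**What to change.** Reconcile 6.5 with the Summary's restart rule. State whether that rule or the opt-back-in rule in 4.1 governs the end of a PEP hold, so that one condition and one type of visit apply throughout the protocol. Say what happens to tablets in hand during the hold. Add PEP holds to 7.10, or cross-refer from there to the agreed text, and say whether PSRT consultation applies. Which rule is adopted is for the clinical team.

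The cost is protocol wording and site training. Depending on the rule chosen, there may be an extra rapid HIV test for a small number of participants; rapid testing is already done at every follow-up visit. The SAP needs no change.
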